LIK066 is a potent dual inhibitor of SGLT1/2, which has been studied in healthy subjects, patients with T2DM, and obese patients with elevated BMI. LIK066 is generally safe and well tolerated in the clinical studies being completed to date. LIK066 has a favorable pharmacokinetic profile (T_{1/2} of 10-16 hours), which allows once daily dosing. LIK066 at 150 mg daily dose (as qd, bid or tid) results in a significant weight loss in obese patients; ~ 6% decrease in body weight was demonstrated after 12 week treatment.

All selective SGLT2 inhibitors being approved in the clinical practice are either not recommended or contraindicated in patients with moderate or severe renal impairment (either eGFR<60; or eGFR<45 mL/min) primarily due to lack of efficacy and certain safety concerns. Dual inhibition of SGLT1 and SGLT2 leads to further caloric wasting of glucose attributed to reduced absorption of glucose from the intestine and enhanced inhibition of glucose reabsorption from the kidneys, which is a major mechanistic differentiation from a selective SGLT2 inhibitor. This study is designed to assess the potential efficacy of LIK066 in patients with moderate or severe chronic kidney disease using 24-hour urinary glucose excretion (UGE₂₄) as the primary surrogate endpoint. The design of this study will also evaluate the PK of LIK066 in patients with reduced renal function. Safety and tolerability of LIK066 at 50 mg qd for 7 days will also be assessed in this patient population with reduced renal function.

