6.2 Treatment arms

This is an open label nonrandomized study. Subjects will be assigned to one of the following 5 treatment arms according to their disease status. All subjects will receive LIK066 50 mg qd before breakfast for 7 days.

- Group 1 (n=10, mild renal impairment)
- Group 2 (n=10, moderate renal impairment grade A)
- Group 3 (n=10, moderate renal impairment grade B)
- Group 4 (n= up to 10, severe renal impairment)
- Group 5 (n=10, subjects with normal renal function)

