11.7 Sample size calculation

The sample size was chosen to provide adequate precision around the estimated mean difference in change from baseline UGE24 between a renal impaired group and the group of normal controls.

After 7 days of treatment of LIK066 15 mg once daily in patients with type-2 diabetes in the first-in-human study LIK066X2101, the mean and standard deviation of the change from baseline in UGE24 was approximately 98 g and 24 g respectively. If we observe similar variability in this study, with 10 enrolled subjects in the mild and moderate renal impaired groups and in the group of normal controls and at least 8 completers in each of these groups, a two-sided 90% CI for the difference of means will extend no more than 22.7 g from the observed difference. As an example, in the renal impairment study for the SGLT2 inhibitor empagliflozin (Macha et al 2014), the observed difference between the moderate impaired group and the normal controls was 42 g, representing a 43% decrease in UGE24. If we see a similar reduction in our study, the CI for the difference would extend to no more than 19.3 g to 64.7 g. We consider this as adequate precision for the estimation of the difference in change from baseline UGE24 between the groups.

[figure not shown]
The sample size also provides adequate precision for a comparison of the primary PK variables between groups. After a single dose of LIK066 50 mg in healthy volunteers in LIK066X2101, the coefficient of variation of the C_{max} of LIK066 was approximately 22%. Assuming similar variability in this study, with at least 8 completers in each group, a two-sided 90% CI for the ratio of means will have a lower bound that extends to no less than 0.81 times the observed ratio and an upper bound to no more than 1.23 times the observed ratio. We consider this as adequate precision for the estimation of the ratio of C_{max} between the groups.

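### The Cmax precision of 0.81–1.23 in Protocol 11.7 assumes 8 completers in every group, which the design does not secure for the severe group; the printed bounds also use 7 rather than 14 degrees of freedom

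*Protocol*

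**What the plan says.** Protocol 11.7 makes two precision statements.

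- **UGE24.** The SD is 24 g and the 90% CI half-width is at most 22.7 g. The groups are named: "with 10 enrolled subjects in the mild and moderate renal impaired groups and in the group of normal controls and at least 8 completers". The severe group is not on the list.
- **Cmax.** The paragraph opens by saying that the sample size also gives adequate precision for comparing the primary PK variables between groups. It takes a CV of about 22% from healthy volunteers and continues: "Assuming similar variability in this study, with at least 8 completers in each group, a two-sided 90% CI for the ratio of means". The factors are 0.81 below and "an upper bound to no more than 1.23 times the observed ratio". No group is excepted.

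On group size, Protocol 6.2 fixes four groups at 10 each but lists "Group 4 (n= up to 10, severe renal impairment". The synopsis, Protocol 3.1 and SAP 1.4 agree. None gives a minimum number of severe patients enrolled or completing. The only lower number, in the synopsis and Protocol 3.1, is that one severe patient must be enrolled before the normal group opens. That rule governs the order of enrolment and sets no floor for the analysis.

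On analysis, Protocol 11.4.2 and SAP 5.3 plan a geometric mean ratio to normal, with two-sided 90% CI and p-value, for every impaired group. They extract it by diabetic status and day. Neither excepts the severe group.

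**The concern.** For four of the five groups, 8 completers is a reasonable working figure, because 10 are to be enrolled. For the severe group nothing in the design supports it. A colleague reading 11.7 would nevertheless credit the severe-versus-normal Cmax ratio with limits of about 20% either way.

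PK by renal function is a primary objective (Protocol 2.1), and severe versus normal is the contrast in which renal function differs most. The UGE24 paragraph leaves the severe group out while the Cmax paragraph does not, so the reader cannot tell whether the difference is deliberate.

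The printed bounds are also wider than a standard two-sample interval at the stated inputs, which raises the question of how they were computed.

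**Working it through.** **Inputs.** CV 22%, two-sided 90% CI and 8 completers per group come from Protocol 11.7, as does the UGE24 SD of 24 g. The number of severe completers is not given, so a range is shown as an assumption. The normal group is taken at 8 completers, as in 11.7.

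**Formula.** Log-scale SD: s = √ln(1 + 0.22²) = 0.2174. CI factors: exp(± t × s × √(1/n₁ + 1/n₂)), where t is the 95th percentile.

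**Reproducing the plan, 8 versus 8.** Here √(1/8 + 1/8) = 0.5.

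- t on 7 df = 1.895: exp(± 1.895 × 0.2174 × 0.5) = 0.814 to 1.229, which is the printed 0.81–1.23.
- t on 14 df = 1.761: 0.826 to 1.211.
- Normal quantile 1.645: 0.836 to 1.196.

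UGE24 follows the same pattern. With 7 df, 1.895 × 24 × 0.5 = 22.7 g, as printed. With 14 df, 1.761 × 24 × 0.5 = 21.1 g. Both figures in 11.7 therefore come from one convention, t on 7 df. Two independent groups of 8 have 8 + 8 − 2 = 14.

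**Severe versus normal, whole groups, 8 controls.** The middle column uses n₁ + n₂ − 2 df. The last column uses the smaller n minus 1, which is the convention the printed figures appear to follow.

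| Severe completers (assumed) | Two-sample t | Smaller n minus 1 |
|---|---|---|
| 8 | 0.83–1.21 | 0.81–1.23 |
| 7 | 0.82–1.22 | 0.80–1.24 |
| 6 | 0.81–1.23 | 0.79–1.27 |
| 5 | 0.80–1.25 | 0.77–1.30 |
| 4 | 0.79–1.27 | 0.73–1.37 |
| 3 | 0.76–1.31 | 0.65–1.54 |
| 2 | 0.73–1.38 | 0.34–2.96 |

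**How far the convention and the control count matter.** With 5 severe completers, 10 controls and a two-sample t, the factors are 0.810–1.235. With 5 severe completers, 8 in each of the other four groups and a residual variance pooled over all five (37 − 5 = 32 df), they are 0.811–1.234. Both are close to the printed bounds.

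**Whole groups versus the planned contrasts.** The PK ratios are extracted by diabetic status. Protocol 3.1 expects about half of each impaired group to have T2DM. If the controls split the same way (an assumption), 8 versus 8 becomes 4 versus 4, and with 6 df (t = 1.943) the factors are exp(± 1.943 × 0.2174 × √(1/4 + 1/4)) = 0.74–1.35.

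**The case against.** The strongest reply is that the Cmax sentence is conditional: it says what precision follows if each group has 8 completers and does not promise that the severe group will. The paragraph before it lists the mild, moderate and normal groups, and the Cmax paragraph may simply carry that list over. This is a possible reading, but the text does not state it. If it is what was meant, the severe PK contrast has no precision statement at all, and the same edit is needed.

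Several stronger inferences are tempting, and the reply is right to resist them.

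- *That 11.7 contains an arithmetic error that flatters the design.* It does not. The bounds are worded as limits, and the 14-df result of 0.83–1.21 lies inside them. The printed 8-versus-8 statement remains true and errs on the safe side.
- *That 6 severe completers is the threshold, and fewer should make the contrast descriptive.* The documents support no such cut-off. Five nearly suffice with 10 controls or with pooled variance, while under the plan's apparent convention even 7 fall short. The plan sets precision and no success criterion, and a 90% CI shows its own width.
- *That the severe group will be small.* No passage forecasts its size, so the rows for 2 to 4 completers are possibilities that the plan leaves open.

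The introduction's statement that "This study is designed to assess the potential efficacy of LIK066 in patients with moderate or severe chronic kidney disease" adds little here, because it concerns UGE24 as a surrogate for efficacy and not Cmax.

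**Conclusion.** The point holds as a matter of what the design secures. Section 11.7 presents 0.81–1.23 as the Cmax precision for comparisons between groups, and the enrolment rules do not assure that for severe versus normal.

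The loss is modest at 6 or 7 severe completers under a two-sample t interval. It becomes material at 4 or fewer: 0.79–1.27 at 4 and 0.73–1.38 at 2. These figures assume the healthy-volunteer CV of 22%, a common variance across groups, 8 normal completers and whole-group comparison. Contrasts by diabetic status will be wider.

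The degrees-of-freedom point is secondary. It makes the printed Cmax and UGE24 figures slightly conservative and changes no conclusion about the other four groups. It matters because a severe-group table needs a stated convention to sit beside them.

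**What to change.** In Protocol 11.7:

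1. Limit the 8-completer Cmax statement to the mild, Grade A moderate, Grade B moderate and normal groups.
2. Name one degrees-of-freedom convention and restate the Cmax and UGE24 figures together on it. With n₁ + n₂ − 2 they become 0.83–1.21 and 21.1 g, and the worked UGE24 example becomes 42 ± 21.1, or 20.9 to 63.1 g, in place of 19.3 to 64.7 g. Changing only the Cmax figure would leave the section on two conventions.
3. Add the severe-versus-normal Cmax bounds by number of severe completers (8 controls, two-sample t): 6 gives 0.81–1.23, 4 gives 0.79–1.27, 3 gives 0.76–1.31 and 2 gives 0.73–1.38. State that these apply to whole groups and that contrasts by diabetic status will be wider.

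No completer cut-off or descriptive-only rule is needed. The cost is a few sentences and a less favourable stated precision for the severe group. No patients, procedures or analyses are added.

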11.8 Power for analysis of key secondary variables

Not applicable.

11.9 Interim analyses

Refer to [Section 3.5](#). Statistical details of the interim analysis will be described in the Statistical Analysis Plan (SAP).

12 Ethical considerations

12.1 Regulatory and ethical compliance

This clinical study was designed and shall be implemented, executed and reported in accordance with the ICH Harmonized Tripartite Guidelines for Good Clinical Practice, with applicable local regulations (including European Directive 2001/20/EC, US Code of Federal Regulations Title 21, and Japanese Ministry of Health, Labor, and Welfare), and with the ethical principles laid down in the Declaration of Helsinki.

12.2 Responsibilities of the investigator and IRB/IEC

Before initiating a trial, the investigator/institution must obtain approval/favorable opinion from the Institutional Review Board/Independent Ethics Committee (IRB/IEC) for the trial protocol, written informed consent form, consent form updates, subject recruitment procedures (e.g. advertisements) and any other written information to be provided to subjects. Prior to study start, the investigator is required to sign a protocol signature page confirming his/her agreement to conduct the study in accordance with these documents and all of the instructions and procedures found in this protocol and to give access to all relevant data and records to Novartis monitors, auditors, Novartis Quality Assurance representatives, designated agents of Novartis, IRBs/IECs, and regulatory authorities as required. If an inspection of the clinical site is requested by a regulatory authority, the investigator must inform Novartis immediately that this request has been made.

For multi-center trials, a Coordinating Investigator will be selected by Novartis around the time of Last Patient Last Visit to be a reviewer and signatory for the clinical study report.

[figure not shown]
12.3 Publication of study protocol and results

The key design elements of this protocol will be posted in a publicly accessible database such as clinicaltrials.gov. In addition, upon study completion and finalization of the study report the results of this trial will be either submitted for publication and/or posted in a publicly accessible database of clinical trial results.

13 Protocol adherence

This protocol defines the study objectives, the study procedures and the data to be collected on study participants. Additional assessments required to ensure safety of subjects should be administered as deemed necessary on a case by case basis. Under no circumstances is an investigator allowed to collect additional data or conduct any additional procedures for any research related purpose involving any investigational drugs under the protocol.

Investigators ascertain they will apply due diligence to avoid protocol deviations. If an investigator feels a protocol deviation would improve the conduct of the study this must be considered a protocol amendment, and unless such an amendment is agreed upon by Novartis and approved by the IRB/IEC and health authorities, where required, it cannot be implemented.

[figure not shown]

New onset ALT or AST elevation accompanied by symptoms	
 ALT or AST > 3 × ULN accompanied by (general) malaise, fatigue, abdominal pain, nausea, or vomiting, or rash, or eosinophilia
Isolated ALT or AST elevation	
 ALT or AST > 8 × ULN 5 × ULN < ALT/AST ≤ 8 × ULN 3 × ULN < ALT/AST ≤ 5 × ULN
Isolated ALP elevation	
 ALP > 2 × ULN (in the absence of known bone pathology)
Others	
 Any clinical event of jaundice (or equivalent term) Any adverse event potentially indicative of liver toxicity

[figure not shown]
Table 15-2 Actions required for Liver Events

Criteria	Actions required
Potential Hy's Law case	
New onset ALT or AST elevation with coagulopathy	
 Discontinue the study treatment immediately Hospitalize, if clinically appropriate
New onset ALT or AST elevation accompanied by symptoms	
 Establish causality
Isolated ALT or AST elevation > 8 × ULN	
 Complete CRFs per liver event guidance
Jaundice	
Isolated ALT or AST elevation > 5 to ≤ 8 × ULN	
 If confirmed, consider interruption or discontinuation of study drug If elevation persists for more than 2 weeks, discontinue the study drug Establish causality Complete CRFs per liver event guidance
Isolated ALT or AST elevation > 3 to ≤ 5 × ULN (patient is asymptomatic)	
 Monitor liver chemistry tests two or three times weekly
Isolated ALP elevation	
 Repeat liver chemistry tests within 48-72 hours If elevation is confirmed, measure fractionated ALP; if >50% is of liver origin, establish hepatic causality Complete CRFs per liver event guidance

Criteria	Actions required
Any AE potentially indicative of liver toxicity	
 • Consider study treatment interruption or discontinuation • Hospitalize if clinically appropriate • Complete CRFs per liver event guidance

Table 15-3 Exclusion of underlying liver disease

Disease	Assessment
Hepatitis A, B, C, E	
 • IgM anti-HAV; HBSAg, IgM anti-HBc, HBV DNA; anti-HCV, HCV RNA, IgM & IgG anti-HEV, HEV RNA
CMV, HSV, EBV infection	
 • IgM & IgG anti-CMV, IgM & IgG anti-HSV; IgM & IgG anti-EBV
Autoimmune hepatitis	
 • ANA & ASMA titers, total IgM, IgG, IgE, IgA
Alcoholic hepatitis	
 • Ethanol history, gGT, MCV, CD-transferrin
Nonalcoholic steatohepatitis	
 • Ultrasound or MRI
Hypoxic/ischemic hepatopathy	
 • Medical history: acute or chronic CHF, hypotension, hypoxia, hepatic venous occlusion. Ultrasound or MRI.
Biliary tract disease	
 • Ultrasound or MRI, ERCP as appropriate.
Wilson disease	
 • Caeruloplasmin
Hemochromatosis	
 • Ferritin, transferrin
Alpha-1-antitrypsin deficiency	
 • Alpha-1-antitrypsin

16 Appendix 2: Specific Renal Alert Criteria and Actions

Table 16-1 Specific Renal Alert Criteria and Actions

Criteria	Action required
Serum creatinine (sCr) increase 25 – 49% compared to baseline	
 Consider causes and possible interventions Follow up within 2-5 days
Serum creatinine increase > 50%	
 Consider causes and possible interventions Repeat assessment within 24-48h if possible Consider drug interruption or discontinuation unless other causes are diagnosed and corrected Consider hospitalization and specialized treatment
Protein-creatinine or albumin-creatinine ratio increase \geq 2-fold or new onset dipstick proteinuria \geq 1+ or Albumin-creatinine ratio (ACR) \geq 30 mg/g or \geq 3 mg/mmol; or Protein-creatinine ratio (PCR) \geq 150 mg/g or >15 mg/mmol	
 Consider causes and possible interventions Assess serum albumin & serum protein Repeat assessment to confirm Consider drug interruption or discontinuation unless other causes are diagnosed and corrected
New hematuria on dipstick	
Assess & document:
 
 Urine sediment microscopy Assess sCr and urine albumin-creatinine ratio Exclude infection, trauma, bleeding from the distal urinary tract/bladder, menstruation Consider bleeding disorder

Additional specialized assessments are available to assess renal function or renal pathology. (Note: In exceptional cases when a nephrologist considers a renal biopsy, it is strongly recommended to make specimen slides available for evaluation by Novartis to potentially identify project-wide patterns of nephrotoxicity.)

Whenever a renal event is identified, a detailed subject history and examination are indicated to identify, document and potentially eliminate risk factors that may have initiated or contributed to the event:

- Blood pressure assessment (after 5 min rest, with an appropriate cuff size)
- Signs and symptoms such as fever, headache, shortness of breath, back or abdominal pain, dysuria, hematuria, dependent or periorbital edema
- Changes in blood pressure, body weight, fluid intake, voiding pattern, or urine output
- Concomitant events or procedures such as trauma, surgical procedures, cardiac or hepatic failure, contrast media or other known nephrotoxin administration, or other potential causes of renal dysfunction, e.g., dehydration, hemorrhage, tumor lysis

Table 16-2 Follow-up of renal events

Action	Follow up
Assess*, document and record in the Case Report Form (CRF) or via electronic data load.	
• Urine dipstick and sediment microscopy• Blood pressure and body weight• Serum creatinine, electrolytes (sodium, potassium, phosphate, calcium), bicarbonate and uric acid• Urine output
Monitor subject regularly (frequency at investigator's discretion) until:	
• Event resolution: (sCr within 10% of baseline or protein-creatinine ratio within 50% of baseline) or 
• Event stabilization: sCr level with $\pm 10\%$ variability over last 6 months or protein-creatinine ratio stabilization at a new level with $\pm 50\%$ variability over last 6 months.

* Urine osmolality: in the absence of diuretics or chronic kidney disease this can be a very sensitive metric for integrated kidney function that requires excellent tubular function. A high urinary osmolality in the setting of an increase in sCr will point toward a "pre-renal" cause rather than tubular toxicity.

*Review and record possible contributing factors to the renal event (co-medications, other co-morbid conditions) and additional diagnostic procedures (MRI etc) in the CRF.

1.1 Scope of document

The RAP documents contain detailed information to aid the production of Statistics & Programming input into the Clinical Study Report (CSR) for trial “**CLIK066B2202**” as well as for the Interim Analysis.

The Statistical analysis plan (SAP) describes the implementation of the statistical analysis planned in the protocol.

1.2 Study reference documentation

Study documents available at the time of finalization of this Statistical Analysis Plan include the study protocol v00, the eCRF (Version 7.0), and the Data Management Plan (Version 4.0).

[figure not shown]
1.3 Study objectives

[figure not shown]
1.3.1 Primary objectives

- To assess the effect of a 7-day treatment with LIK066 on 24-hour urinary glucose excretion (UGE) in subjects with decreased renal function compared to those with normal renal function
 - 24-hour urinary glucose excretion on Day 7
- To assess the pharmacokinetics of LIK066 on Day 1 and Day 7 in subjects with decreased renal function compared to those with normal renal function.
 - C_{max}, T_{max}, AUC_{tau}, AUC_{last}, AUC_{inf}, T_{1/2}, CL/F, V_z/F, CL_r

1.3.2 Secondary objectives

- To assess the safety and tolerability of a 7-day treatment with LIK066 in subjects with decreased renal function compared to those with normal renal function.
 - Adverse events

[figure not shown]
1.4 Study design and treatment

This study employs an open-label, multiple-dose, parallel-group design in patients with varying degrees of decreased renal function (mild, moderate and severe renal impairment) and subjects with normal renal function.

Ten (10) subjects each with mild (eGFR 60-89 ml/min/1.73 m²), Grade A moderate (eGFR 46-59 ml/min/1.73 m²), Grade B moderate (eGFR 30-45 ml/min/1.73 m²), and normal renal function (eGFR ≥90 ml/min/1.73 m²); and up to 10 patients with severe renal impairment (eGFR ≤29 ml/min/1.73 m², not on dialysis) will be enrolled.

As it can be seen from [Figure 1-1](#), each subject will participate in a screening period of up to 28 days, one baseline period, one treatment period of 7 days (including domicile and outpatient visits), a follow-up period, and an end-of-study evaluation approximately 96 hours after the last drug administration.

Figure 1-1: Study Design

Patients with varying degrees of decreased renal function will be enrolled first; subjects with normal renal function will be enrolled after approximately 50% of the patients with decreased

renal function have been enrolled. Because body weight and age are covariates in the estimation of eGFR formula, the 10 subjects with normal renal function will be matched to 10 of the enrolled patients with decreased renal function by age (approximately ± 10 years), weight (approximately $\pm 20\%$), and, if possible, diabetic status. The enrolled patients will be ranked by age and selected, beginning with the youngest and ending with the oldest, in an increment that yields 10 total patients.

Since this is a non-randomized study, subjects will be assigned to one of the following 5 groups according to their disease status. All subjects will receive LIK066 50 mg qd before breakfast for 7 days.

- Group 1 (n=10, mild renal impairment)
- Group 2 (n=10, moderate renal impairment grade A)
- Group 3 (n=10, moderate renal impairment grade B)
- Group 4 (n= up to 10, severe renal impairment)
- Group 5 (n=10, subjects with normal renal function)

2 First interpretable results (FIR)

First interpretable results (FIR) will be provided for this trial.

The study FIR template (mock slides) can be found in CREDI in the study RAP folder Cabinets/CREDI Projects/L/LIK066/CREDI Studies/LIK066B2202/Administrative Files (study level)/RAP or RAMP Meeting/.

The template shows the analysis / results to be presented in the FIR. Study outputs required to be created at the time of the FIR will be highlighted in TFL shells document and marked as “Key” in the Programming Deliverables Tracker (PDT) output list.

FIR will focus on the following analyses:

- Analysis of populations (if needed)
- Subject disposition
- Demographics and baseline characteristics. Baseline characteristics include, but not limited to:
 - Age, Weight/Height/BMI, Diabetes status, UGE24
- Safety results include, but are not limited to:
 - Number and percentage of subjects with adverse events by body system and preferred term with a breakdown by renal function
- Pharmacokinetic (PK) results for plasma:
 - Arithmetic mean (SD) plasma PK concentration-time plot per renal function (overlying).
 - Summary statistics for PK parameters.
- Pharmacodynamic (PD) analyses include, but are not limited to:

- Model estimated renal function comparison in UGE24, change from baseline and % change from baseline in UGE24.
- Arithmetic mean (SD) UGE24 plot per renal function (overlying) over time

3 Interim analyses

An interim analysis may be initiated once approximately half of the enrolled subjects have completed the study. The purpose of the analysis will be to assess the impact of reduced renal function on UGE24 in order to inform development decisions for LIK066. Actions such as early termination of the study should objectives be met, adjustments to the sample size, and/or revisions of the dose may be made.

Additional interim analyses may be conducted to support decision making concerning the current clinical study, the sponsor’s clinical development projects in general or in case of any safety concerns. The clinical team may communicate interim results to relevant Novartis teams for information, consulting and/or decision purposes.

4 Statistical methods: Analysis sets

For all analysis sets, subjects will be analyzed according to the study treatment(s) received.

The safety analysis set will include all subjects that received any study drug.

The PK analysis set will include all subjects with at least one available valid (i.e. not flagged for exclusion) PK concentration measurement, who received any study drug and experienced no protocol deviations that impact on PK data.

The PD analysis set will include all subjects with available PD data, who received any study drug and experienced no protocol deviations with relevant impact on PD data.

The analysis sets and protocol deviation codes are related as follows:

Table 4-1 Protocol deviation codes and analysis sets

Category Deviation code	Text description of deviation	Data exclusion
Subjects are excluded from PD and PK analysis in case of these protocol deviations:		Exclude subject from PD and PK analysis set
COMD01	Subject received prohibited concomitant medication	

If updates to this table are needed, an amendment to the SAP needs to be implemented prior to DBL.

5 Statistical methods for Pharmacokinetic (PK) parameters

All subjects within the PK analysis set will be included in the PK data analysis.

